## 6.8. Storage and analysis of clinical samples

The collection, local processing, storage and transportation of participant samples, including tumour and PBMCs; histopathological quality assurance and processing in the TBR and transportation to Platinum Informatics Ltd. at the School of Life Sciences, University of Dundee, along with return of surplus material to the TBR for storage and additional future analyses, will be detailed in the PROTEAN Clinical Sample Handling Manual, which will be available to all participating sites.

The patient tumour samples and PBMCs (if site is undertaking) will be temporarily stored at the respective collection sites, before transportation to the TBR, at Ninewells Hospital in Dundee.

TBR will catalogue samples and histopathological characterisation and quality assurance checks will be undertaken. Subsequently, tumour specimens will be transported to the School of Life Sciences (SLS), University of Dundee, for neoantigen analysis by Platinum Informatics Ltd. Utilising laboratory facilities at the University of Dundee, SLS, including at the FingerPrints Proteomics and Mass Spectrometry Facility, sample processing, (comprising extract preparation, immunoprecipitation and LC-MS/MS analysis) will be performed according to optimised SOPs established by Platinum Informatics Ltd. Raw MS data will be processed and used by Platinum Informatics for neoantigen identification.

Surplus tumour material will be returned to the TBR for storage and will be available for additional genomic and transcriptomic work, allowing both validation of predicted neoantigens and for additional future proteo-genomic studies undertaken in laboratory facilities at the University of Dundee, SLS with analysis of data undertaken by Platinum Informatics.

PBMC preparations will be used for characterisation of pre-existing T cell responses to identified neoantigens in the Immunoassay Biomarker Core laboratory at Ninewells Hospital and Medical School.

All material will be handled in accordance with the Human Tissue Act 2004 and the 2006 Human Tissue (Scotland). Access to them will be tightly controlled through the CI.

## 6.9. End of study

The end of study at all sites is defined as last participant last visit. The Sponsor, CI and/or the TMG have the right to terminate the study at any time for clinical or administrative reasons.

The end of the study will be reported to the Sponsor, REC and NHS R&D Office(s) within 90 days, or 15 days if the study is terminated prematurely.

A final clinical study report will be published within 1 year of the end of study and will also be provided to the Sponsor and REC.

## 7. STUDY INTERVENTION

There will be no treatment intervention during this study. The study will not interfere with the participant's routine treatment pathway and the participant's standard of care treatment will continue. The participant's care will not be affected by any of the data generated.

## 8. PHARMACOVIGILANCE

### 8.1. Definitions

Term	Definition	
Adverse Event (AE)	Any untoward medical occurrence	
Serious Adverse Event (SAE)	
 
A SAE is any untoward medical occurrence that:
 
results in death
 
is life-threatening
 
requires inpatient hospitalisation or prolongation of existing hospitalisation
 
results in persistent or significant disability/incapacity
 
consists of a congenital anomaly or birth defect
 
Other 'important medical events' may also be considered serious if they jeopardise the participant or require an intervention to prevent one of the above consequences.
 
	
	NOTE: The term "life-threatening" in the definition of "serious" refers to an event in which the participant was at risk of death at the time of the event; it does not refer to an event which hypothetically might have caused death if it were more severe.	

NB: to avoid confusion or misunderstanding of the difference between the terms "serious" and "severe", the following note of clarification is provided: "Severe" is often used to describe intensity of a specific event, which may be of relatively minor medical significance. "Seriousness" is the regulatory definition supplied above.

## 8.2. Operational definitions for (S)AEs

As this study involves the collection of blood and tissue samples with no intervention, AEs will only be recorded where, in the opinion of the CI/PI, they are directly associated with the collection of these samples. AEs occurring during the collection of samples, where this is being done at the same time as a standard care procedure, will only be recorded if, in the opinion of the CI/PI, this is directly associated with the additional sampling required for the study.

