#### Biopsy

- A fresh tumour biopsy will be collected:
  - Prior to the commencement of any subsequent scheduled anticancer treatments\*;
     OR
  - After the completion of the latest line of anticancer treatment\*; OR
  - During follow up when a participant is not receiving or is between scheduled anticancer treatments\*.

\*Anti-cancer treatments excluding surgery

- The biopsy may be obtained from any site of tumour, primary or metastatic as considered the most appropriate and feasible at the time of the procedure.
- Biopsies from more than one tumour site may be obtained at the same time point and procedure, but this is not mandatory, only biopsy of a single tumour site is required for study participation.
- Up to 10 biopsies, approximately 2mm each, will be taken at each timepoint and if tumour biopsy is being undertaken by endoscopy 2 biopsies approximately 2mm each of adjacent normal oesophageal or gastric mucosa.
- As far as possible, tumour biopsies for the study will be obtained during routine clinical care procedures e.g. endoscopy, surgery, stenting. However, where this is not possible, consent will be requested for study specific procedures for biopsy to obtain tumour material.
- Participants may provide additional consent for further biopsies during further routine clinical care procedures to be taken as an optional part of the study.
- Details of sample collection, processing, storage and transfer will be provided in PROTEAN Clinical Sample Handling Manual.

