#### 8.3. Recording and reporting of AEs/SAEs

All AEs will be recorded on the AE Log in the electronic case report form (eCRF) and will be assessed for severity by the CI or PI. AEs will be recorded from the time a participant consents to join the study until the participant's last study visit. An AE may be classified as a SAE.

AEs/SAEs will be followed up until recovered/recovered with sequelae/death/30 days after participant's last visit - whichever is the soonest.

**SAEs which are both unexpected and related to study participation** will be submitted on an HRA non-CTIMP Safety Report form to the REC by the CI, within 15 days of becoming aware of the SAE, and copied to the Sponsor Research Governance Office.

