## 15.4. Appendix 4 – Schedule of Procedures

Visits				
V1 a	V2ª	V3 bc	V4 bc	V5 b
Screening	Day 1 Up to 28 days post screening	Week 6 +/- 7 days	Week 12 +/- 7 days	Week 18 +/- 7 days
Х				
Х				
Х				
Х				
Х				
Х	х	Х	Х	Х
	х			
		X A maximum of 3 further research biopsy samples may be collected between day 1 and week 18		ected
	х			Х
		X A maximum of 2 further research blood samples may be collected between day 1 and week 18		
	Х	Х	Х	Х
	х	Х	Х	Х
	V1 a Screening X X X X X X X X	V1aV2aScreeningDay 1Up to 28 days post screeningXX	V1aV2aV3bcScreeningDay 1 Up to 28 days post screeningWeek 6 +/- 7 daysXX	V1aV2aV3bcV4bcScreeningDay 1 Up to 28 days post screeningWeek 6 +/- 7 daysWeek 12 +/- 7 daysXImage: ScreeningXImage: ScreeningXImage: ScreeningImage: ScreeningImage: ScreeningXImage: ScreeningImage: ScreeningI

a Visits 1 & 2 may be combined

b Visits will be conducted at the same time as standard care procedures and may not fall in line with visit windows, this will not be considered a breach.

c May be by telephone if participant is not attending a standard care clinic visit.

Activity	Responsibility	Timing	Comments
Review for AEs	Trial staff	Each visit	Recorded on eCRF
			system.
Review of recorded	PI (or delegate)	Within 10 days of	Recorded on eCRF
AEs for relatedness		recording	and/or medical
and seriousness			records.
Reporting SAEs:	PI (or delegate)	Within 10 days of	SAE form:
All SAEs need to be		becoming aware of	Non-CTIMP safety
assessed by the PI		SAE	report
or delegated doctor.			Report to:
			CI
			TCTU Trial Manager
Reporting SAEs:	CI	Within 15 days of PI	Report to:
All SAEs need to be	TCTU Trial Manager	becoming aware of	REC
signed off by the CI.		SAE	Sponsor

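### Section 8.2 makes a judgement of relatedness the condition for recording an adverse event, while the safety table judges relatedness after recording, so complications of uncertain cause at combined procedures can miss the AE log

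*Protocol*

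**What the plan says.** Four places in the protocol govern the recording of adverse events.

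- **Section 8.1** defines an adverse event as "Any untoward medical occurrence", with no causal element.
- **Section 8.2**, whose heading covers both AEs and SAEs, restricts this: "AEs will only be recorded where, in the opinion of the CI/PI, they are directly associated with the collection of these samples". When sampling coincides with a standard care procedure, an event "will only be recorded if, in the opinion of the CI/PI, this is directly associated with the additional sampling required for the study". The stated reason is that the study takes samples and gives no intervention.
- **Section 8.3** says that all AEs go on the AE Log in the eCRF and are assessed for severity, from consent to the last study visit. At the reporting step it applies a separate filter: the REC is sent "SAEs which are both unexpected and related to study participation".
- **The safety table at the end of Appendix 4** starts with "Review for AEs" by trial staff at each visit, recorded on the eCRF system. Its next row has the PI or a delegate review recorded "AEs for relatedness" and seriousness within 10 days of recording. Further rows cover SAEs, with assessment by the PI or a delegated doctor and sign-off by the CI.

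On the procedures themselves, section 6.4 (Biopsy) says: "As far as possible, tumour biopsies for the study will be obtained during routine clinical care procedures". Appendix 1 names tumour biopsy as the main risk to participants and says that complications become more likely with multiple biopsies.

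**The concern.** Section 8.2 and the safety table put the causality judgement at different points. In 8.2 it comes first and decides whether an entry exists. In the table it comes second and is made on entries that already exist. A site cannot tell whether trial staff may log an event before the CI or PI has given an opinion on it.

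The difference matters most where cause is hard to assign. When research pieces are taken alongside routine ones, or during surgery or stenting, a bleed or infection may have no single identifiable source. Section 8.2 has no category for that situation, and its test for combined procedures is the narrower one. At stake is how complete the AE log is for the study's main risk. The CI's ongoing risk/benefit review under section 8.4 would be expected to draw on that log.

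**Working it through.** No arithmetic decides this point, and the protocol states no complication rate to reproduce. The check sets the two sequences side by side.

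**Step 1: what the log contains under each rule.** Under 8.2 the recorded events are exactly those that the CI or PI already considers directly associated with sampling. Under the table they are the events that trial staff find at visits.

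**Step 2: what the later relatedness review can do.** If the log holds only events already judged associated, the review can confirm them, downgrade some and assess seriousness. It cannot add an event, because an event judged unassociated has no entry to review. If the log holds events before judgement, the review can sort them in either direction.

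**Step 3: how typical events fare at a combined procedure.**

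| Event | 8.2 followed as written | Table's order |
|---|---|---|
| Clearly due to the research pieces | Recorded | Recorded, then judged related |
| Clearly due to the routine procedure | Not recorded | Recorded if found, then judged unrelated |
| Cause cannot be separated | Not recorded unless direct association is positively judged | Recorded, then reviewed |
| Judged unrelated in error | Not recorded, so not reviewable from the log | Recorded, and correctable at review |

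The last two rows are where the sequences produce different safety information on sampling.

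**Step 4: how much of the study the narrower test covers.** Section 6.4 makes the combined procedure the preferred route, so the narrower test applies to the route most biopsies are meant to take. Section 6.4 allows up to 10 tumour pieces per timepoint, plus 2 pieces of adjacent normal mucosa when the tumour biopsy is endoscopic: 10 + 2 = 12 research pieces at one endoscopy. The research contribution is therefore not trivial beside the routine one.

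**Step 5: whether another process would catch the gap.** Appendix 1 answers nil to additional processes such as a data monitoring committee or independent data review. Section 11.1 says only that the study may be selected for audit or monitoring. The SAE rows of the table add reviewers, and their clock runs from awareness of the event rather than from a log entry. They could catch serious events. But the heading of 8.2 covers SAEs too, and the protocol does not say whether its filter applies before those rows.

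**The case against.** Restricting recording to sampling-related events is a deliberate choice with a stated reason, and it is sensible in a study without a treatment intervention. That stands: the restriction alone is not an error.

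Several stronger readings are tempting, and the documents do not support them.

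- *Sections 8.2 and 8.3 contradict each other outright.* Section 8.2 sets operational definitions, and 8.3 can be read as logging all AEs so defined. The firm conflict is between 8.2 and the safety table.
- *Unrecorded events leave no trace or cannot be audited.* Medical records are the source data and are flagged for study participation (10.1). The Sponsor and REC have direct access to source documents in an audit (10.2). The table also allows the relatedness review to be documented in the medical records. The supportable statement is that an event may be missing from the eCRF AE log.
- *Delayed complications are excluded because 8.2 speaks of events during collection.* Its first sentence has no timing limit, and recording runs to the last visit.
- *Causality is judged only once and the later review is empty.* The review can downgrade events and assesses seriousness, and the SAE rows bring in further reviewers.
- *A complication rate is biased by a calculable amount.* The protocol gives neither a rate nor the share of combined procedures. Comparing the rate for a whole combined procedure with the rate attributed to the extra pieces would also compare different quantities. A complication rate is neither an endpoint (2.1) nor a planned analysis (9.3).

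These points limit the concern but do not remove it. None says when causality is to be judged, or what a site does with a complication whose cause it cannot separate.

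**Conclusion.** The concern holds as a conflict of sequence with a practical consequence. Followed as written, 8.2 keeps complications of indeterminate cause out of the AE log, and the review described in the safety table cannot bring them back. The preferred route for biopsies is the one most exposed.

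The consequence is possible under-ascertainment of sampling-related complications in the eCRF log and in what the CI sees under 8.4. Its size cannot be derived from the document. No primary or secondary outcome, sample size or error rate is affected. The conclusion assumes that sites apply 8.2 literally; a site that follows the table would log such events. That two sites could both comply and record different events is reason enough to reconcile the passages.

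**What to change.** Reconcile 8.2, 8.3 and the safety table to the order that the table already sets out.

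1. In 8.2, record on the AE Log any untoward event that is plausibly a complication of a procedure at which a research sample was taken. Trial staff may make the entry before causality is judged.
2. The PI or delegate then assigns relatedness on the eCRF, within the table's existing 10 days, using three options: research sampling, routine procedure, or cannot be separated.
3. Events in the third category are shown to the CI for review. They should not be classed as related automatically, since that would count indeterminate complications of routine surgery or stenting as study harm.
4. In 8.3, say that all AEs meeting the 8.2 recording rule are logged, and state that the SAE rows of the table apply without a prior relatedness filter.
5. Leave disease and treatment events unconnected with the procedure unrecorded, and keep the related-and-unexpected filter at REC reporting.

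The cost is limited rewording, one eCRF field and a few more log entries, some of which will finally be attributed to routine care. Recording changes; clinical management does not.

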#### 8.3. Recording and reporting of AEs/SAEs

All AEs will be recorded on the AE Log in the electronic case report form (eCRF) and will be assessed for severity by the CI or PI. AEs will be recorded from the time a participant consents to join the study until the participant's last study visit. An AE may be classified as a SAE.

AEs/SAEs will be followed up until recovered/recovered with sequelae/death/30 days after participant's last visit - whichever is the soonest.

**SAEs which are both unexpected and related to study participation** will be submitted on an HRA non-CTIMP Safety Report form to the REC by the CI, within 15 days of becoming aware of the SAE, and copied to the Sponsor Research Governance Office.

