#### VIII. STUDY FLOW CHART

\*Treatment can be planned to occur subsequently or recently completed. Eligible participant may be pre-, post- or between treatments.

\*May be by telephone if participant is not attending a standard of care clinic visit.

¥A maximum of 2 additional optional research blood samples and 3 research biopsy samples may be collected. This includes during standard of care procedures at any time during the study period and also research biopsy / PBMC up to 28 days after radiological and/or clinical progression.

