#### Justification:

The main risk for participants is from the biopsy of tumour tissue. Where possible this will be done at the same time as standard care biopsy or tumour resection.

What are the key risks related to assessments you plan to undertake in this study?			
Intervention	Hazard	How will these risks be minimised?	
Blood samples	Discomforts of drawing blood include temporary discomfort from the needle stick, the possibility of pain or bruising at the site of the blood draw, occasional feelings of light headedness and, rarely, infection at the site of the blood draw	Blood samples will be taken at the same time as blood draw for routine care purposes whenever possible. Staff taking blood will be experienced in venepuncture.	
Biopsy	Risk of serious complications, such as bleeding, pneumothorax, infection, or even death, depending on the site of disease. Risks vary according to the technical aspects of the biopsy (e.g. size of needle and location or size of the required specimen), the experience or training of the medical professional performing the biopsy, and participant characteristics. The risks for both major complications and AEs increase with multiple biopsies.	Previously collected samples will be used when available, or samples will be taken at the same time as clinically indicated procedures whenever possible. In other instances, the biopsies will be only performed if the risk to the participant is low or moderate. Only samples at baseline are required as per protocol, other samples will only be collected as far as possible during standard care procedures. In considering the study design we have reflected upon the key ethical guidance on research biopsies in cancer research provided in the American Society of Clinical Oncology Research Statement: Ethical Framework for Including Research Biopsies in Oncology Clinical Trials. Journal of Clinical Oncology 37, no. 26 (September 10,	

	2019)2368-2377. Our approach in this study is consistent with this guidance and accordingly is consistent with the practice of oncology studies of this type in a global context.
Outline any other processes that have been put in place (e.g. DMC, independent data review, etc.) Nil	to mitigate risks to participant safety

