### 15.5. Appendix 5 – Safety Reporting Flow Chart

#### Unexpected Serious Related AE

MUST be reported to REC within 15 days of Trial team/Investigator becoming aware of the event

- Using the non-CTIMP Safety report to REC form (HRA website)
- Sponsor needs to be notified via email to [contact]
- Record in AE Log/CRF

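### Adverse event recording stops at the last study visit, although late optional research samples may be taken at that visit and, by the flow chart, after it; the 15-day ethics committee clock also starts differently in three places

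*Protocol*

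**What the plan says.** **Which events are recorded, and until when.** Section 8.2 restricts recording to harms of sampling: "AEs will only be recorded where, in the opinion of the CI/PI, they are directly associated with the collection of these samples". Section 8.3 sets the period: "AEs will be recorded from the time a participant consents to join the study until the participant's last study visit". A separate sentence in 8.3 deals with follow-up: "AEs/SAEs will be followed up until recovered/recovered with sequelae/death/30 days after participant's last visit - whichever is the soonest".

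**When samples may be taken.** The Appendix 4 schedule states for biopsies "A maximum of 3 further research biopsy samples may be collected between day 1 and week 18" and for blood "A maximum of 2 further research blood samples may be collected between day 1 and week 18". V5, the last visit, is at week 18 with a window of 7 days either side. The table is damaged in the text at hand, but it appears to show a research blood at V5. The study flow chart footnote allows additional samples during the study period and adds "research biopsy / PBMC up to 28 days after radiological and/or clinical progression".

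**The risk.** The justification in Appendix 1 says "The main risk for participants is from the biopsy of tumour tissue". It lists bleeding, infection, pneumothorax and death among the possible complications, says that risk rises with multiple biopsies, and states that only the baseline samples are required.

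**Reporting of serious events.** Section 8.3 has the CI report unexpected, related SAEs to the REC within 15 days of awareness, without saying whose awareness. The reporting table after the Appendix 4 schedule gives the PI 10 days from recording to judge relatedness and seriousness. It gives the PI 10 days from awareness of an SAE to report to the CI and the trial manager. It gives 15 days from the PI's awareness for the report to the REC and sponsor. Appendix 5 says such an event "MUST be reported to REC within 15 days of Trial team/Investigator becoming aware of the event".

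**The concern.** The only adverse events this study records are those caused by its own sampling, so the recording window should follow the sampling. It follows the visit calendar instead. Bleeding or infection can begin after a procedure, and a sample taken at or after the last visit has no recording time behind it. Appendix 1 names no other process for mitigating safety risk, and Section 8.4 gives the CI an ongoing review of risk and benefit. AE recording is therefore the main stated source for that review.

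The two sampling windows also conflict. Appendix 4 ends optional sampling at week 18, while the flow chart allows a period tied to progression that can run beyond it. Section 6.9 ends the study at the last participant's last visit, so a post-progression sample in that participant could fall after the study has ended.

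For serious events, a site that keeps to the reporting table could still miss the Appendix 5 limit, because the two start the clock at different people's awareness.

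**Working it through.** The protocol gives no figure of its own to reproduce. The check is timeline arithmetic on its day counts.

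**Recording window against sampling window**

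Inputs: V5 at week 18 ± 7 days (Appendix 4); sampling to 28 days after progression (flow chart); recording to the last visit and follow-up to at most 30 days after it (Section 8.3). Assumptions: V5 is the last study visit, and progression is found at V5.

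| Quantity | V5 on time | V5 at end of window |
|---|---|---|
| Last visit; recording closes | 18 × 7 = day 126 | 126 + 7 = day 133 |
| Last permitted sample (flow chart) | 126 + 28 = day 154 (week 22) | 133 + 28 = day 161 (week 23) |
| Permitted sampling with no recording | 154 − 126 = 28 days | 161 − 133 = 28 days |
| Latest follow-up under 8.3 | 126 + 30 = day 156 | 133 + 30 = day 163 |

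- Sample taken at V5: 0 days of recording afterwards. This rests on Appendix 4 alone.
- Sample taken after V5: recording is already closed. This rests on the flow chart footnote alone.
- Required baseline biopsy on day 1: about 18 weeks of recording afterwards, so no gap.
- Moving the end of recording to 30 days after the last visit would still leave only 156 − 154 = 2 days after the latest permitted sample. The anchor has to include the last sample.

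The follow-up sentence does not close the gap. It says how long events are pursued. It does not say that an event starting after the last visit is to be recorded.

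**Reporting of serious events**

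Inputs: PI review within 10 days of recording; PI report within 10 days of awareness; REC report within 15 days of PI awareness (reporting table); REC report within 15 days of trial team or investigator awareness (Appendix 5).

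| Scenario | CI told by | REC told by | Against 15 days |
|---|---|---|---|
| (a) PI aware on day 0 | day 10 | day 15 | Met; 15 − 10 = 5 days left for the CI |
| (b) Staff record on day 0; PI recognises the event as serious at review on day 10 | 10 + 10 = day 20 | 10 + 15 = day 25 | REC report 10 days past Appendix 5; CI told 5 days after that limit |
| (c) PI aware on day 0; the 8.3 clock read as CI awareness | day 10 | 10 + 15 = day 25 | 10 days past the table and Appendix 5 |

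**The case against.** The case on the other side is substantial, and parts of it stand.

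- **A reader might infer that complications of biopsy in general go unrecorded.** The documents do not support this. The only required biopsy is at baseline and has about 18 weeks of recording. The gap concerns late samples, mostly optional, which Appendix 1 says are taken as far as possible during standard care.
- **Sampling after V5 rests on one footnote.** Appendix 4 stops at week 18. Section 8.3 refers to the last study visit rather than to week 18, visits may fall outside their windows, and nothing says that attending for a post-progression biopsy is not a study visit. If it counts as one, recording stays open through it. Even then, recording would close on the day of the sample, so delayed onset would still be missed.
- **A reader might infer that the reporting table always takes 20 days to reach the CI.** It does not. Scenario (a) fits within 15 days. Section 8.2 also makes recording depend on the opinion of the CI or PI, so the PI will often know of the event at or before recording. What stands is that the clock starts differ and scenario (b) is permitted.
- **A reader might infer that every SAE goes to the REC.** In the table, the reference to all SAEs attaches to sign-off by the CI. Section 8.3 and Appendix 5 agree on unexpected, related events. The table's wording needs only to be aligned with them.
- **A reader might infer a biased complication rate.** No safety rate is an objective or endpoint, so no primary or secondary result changes.

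**Conclusion.** The point holds in a limited form. As written, complications that begin after the last visit from a late research sample fall outside the recording rule. Recording time is zero after a V5 sample, and up to 28 days of sampling permitted by the flow chart follow the close of recording. The 28-day figure assumes that progression is found at V5, that V5 is the last study visit, and that the flow chart window applies beyond week 18. The zero-day figure does not need the flow chart. The number of participants with late samples is not given, so the number of missed events cannot be estimated. The matter is one of participant safety oversight, not of the study's results.

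The secondary point is firm only as an inconsistency. Section 8.3, the reporting table and Appendix 5 do not share a clock start, so a site can meet the table and be up to 10 days late under Appendix 5. This happens only when the PI's recognition of seriousness lags behind recording by staff.

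**What to change.** 1. In Section 8.3, record sampling-related AEs until 30 days after the later of the last research sample and the last study visit. Thirty days is the period 8.3 already uses for follow-up. Run the follow-up clause from the same anchor, so that an event first recorded late can still be followed.
2. Reconcile the flow chart footnote with Appendix 4 on whether research sampling may go past week 18, and say whether attendance for such a sample counts as a study visit.
3. Give one start for the 15-day REC clock in Section 8.3, the reporting table and Appendix 5, with the internal review and reporting steps fitting inside 15 days from that start.
4. Word the CI row of the reporting table so that REC reporting covers unexpected, related SAEs, as in Section 8.3 and Appendix 5.

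The cost is a text amendment and one telephone call or record check per participant. No study procedure is added.
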